### Safety-population (SP)

Includes all subjects who were randomized.

Assignment of patients to analysis populations will be done during the data review meeting. Primary analysis will be based on the ITT population; an additional analysis on PP will be performed to assess validity of results. Safety analyses will be performed on the SP.

The primary endpoint measured at 90 days will be analyzed on an intention to treat basis. It is anticipated that there may be some "crossover" from the intervention group to the control group or from the control group to the intervention group. The number of crossovers will be documented to provide context for interpreting the primary results; however, treatment crossovers will be analyzed according to the intention to treat principle and thus will be included in the arm to which they were randomized.

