### Safety endpoints:

[figure not shown]
- 1. Increase in serum creatinine by 26.5  $\mu$ mol/L (0.3 mg/dL) or more and/or a  $\geq$ 25% increase in serum creatinine OR a  $\geq$ 20% drop in GFR) at discharge
- 2. Access-related complications (bleeding, infection)

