### 1. STATISTICS

### **1.1. PRIMARY ANALYSIS**

The primary endpoint of the trial is the composite of cardiovascular mortality in 90 days after randomization or a heart failure event in the 90 days after discharge.

The primary analysis of the effectiveness of the UF treatment will be conducted in the ITT population (see section 1.5). The occurrence of cardiovascular deaths or heart failure event after discharge from hospital will be summarized using event proportions, i.e. number of patients with an event divided by the number of patients randomized to the respective treatment group.

The null hypothesis of no difference in event proportions between the randomized groups will be tested in a two sided test using logistic regression analysis adjusting for stratification variables (other than study site). Odds ratios including 95% confidence intervals (CI) will be presented as well as p-values (Wald methodology). In addition, descriptive analyses of the components of the primary outcome will be reported in the form of Kaplan-Meier (KM) curves for the time-to-event for each of cardiovascular mortality in 90 days after randomization and heart failure event within 90 days after discharge (Kaplan and Meier, 1958). Follow-up times will be censored at date of death, loss to follow-up or at the 90 day cut-off period.

Hazard ratios comparing the two treatment groups under study will be determined within the Cox proportional hazard model and provided along with the 95% HR confidence limits (Wald-CI).

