### **1.3.** SAFETY ANALYSES

Standard procedures for reporting of adverse events will be used. Adverse events will be summarized as frequencies and percentages by treatment group.

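### No safety summary by treatment received is planned although crossover is foreseen, so ultrafiltration access complications may be understated

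*Combined protocol and SAP*

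**What the plan says.** Section 1.5 of the combined protocol and SAP sets membership of the safety population by randomisation alone: "Includes all subjects who were randomized". It adds: "Safety analyses will be performed on the SP". Section 1.3 gives the method: "Adverse events will be summarized as frequencies and percentages by treatment group". Section 1.1 uses the same term for the randomised group when it defines the primary event proportion, with the denominator "number of patients randomized to the respective treatment group".

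The synopsis names two safety endpoints. One is a renal-function measure at discharge. The other is "Access-related complications (bleeding, infection").

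The end of Section 1.5 says that some patients may cross over "from the intervention group to the control group or from the control group to the intervention group", and that such patients "will be included in the arm to which they were randomized". That paragraph opens with the primary endpoint. Section 1.6 budgets 13% for crossover as a single figure.

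No section provides a safety grouping by treatment received, a summary of UF-exposed patients, or a rule for patients who receive both treatments. The per-protocol repeat in Section 1.4 covers primary and secondary endpoints only.

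**The concern.** Keeping patients in their randomised arm is usually the cautious choice for a superiority claim on efficacy. For a harm caused by the device it works the other way. When exposure and allocation differ, the contrast between arms shrinks and the device looks safer than it is.

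Two mechanisms are possible here. A UF-arm patient who never starts UF adds to the denominator without being at risk from UF. A control patient who crosses to UF and then has an access bleed or infection puts a UF complication in the control column. The second needs crossover "from the control group to the intervention group", which Section 1.5 explicitly foresees. The endpoint affected is one of only two named safety endpoints.

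**Working it through.** **The plan's own figure.** Section 1.6 uses a two-sided Z test with unpooled variance, alpha 0.05, power 0.90, and event proportions of 27% and 16.88%.

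- n per arm = (1.960 + 1.282)² × [0.27 × 0.73 + 0.1688 × 0.8312] / (0.27 − 0.1688)² = 346.2, rounded up to 347, so 694 in total, as stated.
- Loss to follow-up: 694 × 1.10 = 763.4, rounded up to 764.
- Crossover: 764 × 1.13 = 863.3, rounded up to 864, or 432 per arm.

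The stated 864 is reproduced. The 13% enters as one multiplier on the total. Section 1.6 does not say how it divides by direction.

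**Effect on the safety contrast.** Let a and b be the access-complication risks with and without UF. Let c1 be the share of the UF arm that never starts UF, and c0 the share of the control arm that receives UF.

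- UF arm as randomised: (1 − c1)a + c1·b
- Control arm as randomised: (1 − c0)b + c0·a
- Difference: (1 − c1 − c0)(a − b)

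The visible fraction of the true excess depends only on c1 + c0.

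**Inputs.** The documents give no value for a or b. The example takes a = 10% and b = 0, both assumptions, with 432 patients per arm.

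| Scenario | c1 | c0 | UF arm | Control arm | Difference (points) | Visible | UF cases under control |
|---|---|---|---|---|---|---|---|
| UF to control only | 13% | 0 | 8.70% | 0% | 8.7 | 87% | 0 |
| Split equally | 6.5% | 6.5% | 9.35% | 0.65% | 8.7 | 87% | 2.8 |
| Control to UF only | 0 | 13% | 10.00% | 1.30% | 8.7 | 87% | 5.6 |
| 13% of each arm | 13% | 13% | 8.70% | 1.30% | 7.4 | 74% | 5.6 |

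Cases under control are 432 × c0 × a; for example, 432 × 0.13 × 0.10 = 5.6.

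The first three rows have arm shares adding to 13%. If 13% were instead meant as a share of all 864 patients, that would be about 112 patients (864 × 0.13), and 112/432 gives c1 + c0 = 26%, as in the last row.

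**Range.** With b = 0, a = 5% gives a visible difference of 4.35 points (3.7 in the last row) instead of 5. With a = 20% it is 17.4 (14.8) instead of 20. With a = 10% and b = 1%, it is 7.83 (6.66) instead of 9. The visible fractions stay at 87% and 74%.

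**Direction of the error in these figures.** The table treats every UF-arm crossover as never exposed. The synopsis allows 1 to 7 sessions, and Section 1.6 places crossover within the treatment period. A patient who has one session and then switches is still exposed and dilutes nothing. For a given crossover share, 87% and 74% are therefore lower limits on what remains visible.

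**The case against.** A reader might infer that the plan orders UF harms to be charged to control. It does not say so. Section 1.5 states who is in the safety population, not the column in which they are counted. The sentence keeping crossovers in their randomised arm is about the primary endpoint, and Section 1.2 leaves detailed methods and table formats to the SAP. This stands as a limit on wording: as-randomised safety tables are the natural reading, not an explicit instruction. It does not remove the gap, because no section supplies any other rule.

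A reader might also take 7.4 points against 10 as the expected loss. The documents do not support that. They give one 13% figure without a split, no count of UF-arm patients who never start, and no complication rate. Nor do they restrict access complications to UF access, and control patients receive IV diuretics, so b = 0 is an assumption.

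The strongest objection is to making treatment received the main grouping for all adverse events. Crossover probably follows clinical course, so that comparison would be confounded. Without a timing rule, a control patient's event before crossing would be charged to UF. Both points stand, and the remedy should be confined to access and device events.

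Finally, safety reporting is descriptive. No test or margin depends on the grouping, and Section 1.7 gives the DMC adverse event listings and event rates. This lowers the severity. It does not correct the final table.

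**Conclusion.** The point holds in a limited form. The plan foresees crossover in both directions but has no safety summary by treatment received. Read naturally, its tables would understate the excess of access complications under UF and could place some of them in the control column.

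The understatement is at most 13% of the true excess if the arm shares add to 13%, and at most 26% in the upper-bound scenario of 13% of each arm. UF cases appear under control only if control patients cross to UF. The fractions assume that crossover is unrelated to a patient's risk of a complication; the percentage-point figures also rest on the assumed a and b.

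The documents do not support the stronger conclusions that the safety comparison is invalid or that the as-randomised table should be replaced. The primary analysis and the sample size are unaffected. This is a cheap improvement.

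**What to change.** 1. State in Sections 1.3 and 1.5 that adverse events are tabulated by randomised arm, and keep that table for all adverse events.
2. Add a prespecified table by treatment received (any UF session started versus none) for access-related complications and device-related events. A UF-arm patient who starts a session and later switches stays in the UF column.
3. For control patients who cross over, count an event under UF only if it occurs after the first UF session starts. Earlier events stay in the column without UF. Give the denominator of each column.
4. Report crossovers by direction, and the number of UF-arm patients who never started a session, beside both tables.

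The cost is a few lines of SAP text and one extra table, drawing on adverse event and crossover data that the plan already calls for, plus session start times. The downside is that the added comparison is not protected by randomisation. It should be labelled so and read beside the as-randomised table.

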### STUDY SYNOPSIS

Title:	PURE-HF: P eripheral U ltrafiltration for the RE lief from Congestion in H eart F ailure			
Study code:	UF-HF-02-INT			
Study design:	Multicenter, prospective, randomized, parallel-group controlled clinical trial			
Investigational device:	Chiara, peripheral ultrafiltration			
Control device:	not applicable			
Control therapy:	Usual care including high-dose intravenous (IV) diuretics			
Study objectives:	Primary objective			
	To evaluate whether tailored, peripheral ultrafiltration complementary to low-dose diuretics is associated with a reduction in cardiovascular mortality in 90 days after randomization and heart failure events in 90 days after discharge compared to usual care including stepped intravenous diuretics, in acutely decompensated chronic heart failure with fluid overload (not fully responsive to diuretic therapy).			
	Secondary objective			
	The secondary aims will be to examine the effect of the above treatment assignments on:			
	
 
Heart failure rehospitalization analyzed as a recurrent event in 90 days after discharge
 
			
	2. Time until first HF rehospitalization in 90 days after discharge			
	3. Time until first urgent HF visit in 90 days after discharge			
	
 
Quality of life (Patient Global Assessment at baseline, discharge, FU30, FU90; Short Kansas City Cardiomyopathy Questionnaire and EQ-5D-5L at discharge, FU30, FU90)
 
			
	5. Days alive and out of hospital up to 90 days after discharge			
	6. Cardiovascular mortality in 90 days after randomization			
	
 
Resolution of congestion defined as resolution of at least two of the final eligibility criteria present at randomization (this does not include chest x-ray criterion, i.e. if x-ray criterion was one out of two final eligibility criteria, only resolution of the other criterion is necessary), thus:
 
			
	• Jugular venous pressure of $< 8$ cm H 2 O			
	No orthopnea			
	Trace or no peripheral edema			
	
 
Respiratory rate no longer ≥20/minute
 
			
	8. In-hospital worsening heart failure until discharge			
	9. Weight loss at 96h after randomization and at discharge			

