### Per-protocol-population (PP)

Includes all subjects who entered the study in accordance with both the inclusion / exclusion criteria without major protocol deviations and who finished the study in accordance with the study protocol.

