### (Modified) Intention-to-treat population (ITT=FAS)

Includes all subjects who were randomized and for whom complete efficacy data are available. We will analyze subjects lost to follow up based on subjects' status at time of withdrawal of consent and add a sensitivity analysis using multiple imputation for those with missing outcomes at 90 days.

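### The primary ITT set is limited to patients with complete efficacy data and filled at a data review meeting, against the all-randomised denominator in section 1.1

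*Combined protocol and SAP*

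**What the plan says.** Four statements bear on who is in the primary analysis.

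- Section 1.5, (Modified) Intention-to-treat population, defines the set: "Includes all subjects who were randomized and for whom complete efficacy data are available".
- The next sentence there covers losses: "We will analyze subjects lost to follow up based on subjects' status at time of withdrawal of consent". It adds multiple imputation as a sensitivity analysis.
- Section 1.1 sets the event proportion as the "number of patients with an event divided by the number of patients randomized to the respective treatment group".
- Section 1.5, under the safety population, says: "Assignment of patients to analysis populations will be done during the data review meeting". It continues: "Primary analysis will be based on the ITT population; an additional analysis on PP will be performed to assess validity of results".

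The per-protocol set takes patients "without major protocol deviations and who finished the study in accordance with the study protocol". What makes a deviation major is not defined. The synopsis describes a "Multicenter, prospective, randomized, parallel-group controlled clinical trial" and mentions no blinding. One arm receives ultrafiltration sessions and the other high-dose diuretics.

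**The concern.** Whether a patient's efficacy data are complete is known only after randomisation, and it can depend on treatment and outcome. A set defined that way is not an intention-to-treat set, whatever its label. If the arms differ in how many patients are lost, or in who is lost, dropping them changes the comparison that randomisation set up.

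The plan also gives three answers for a patient lost without an event. The definition leaves the patient out. The sentence after it keeps the patient in, with status at withdrawal. Section 1.1 counts the patient in the denominator. The only procedure the plan offers for settling membership is the data review meeting. Judging completeness means looking at efficacy data, and treatment records would show the arm. Nothing in the text says that either is hidden, or whether the meeting comes before database lock. Exclusions made there could not later be shown to be independent of outcome.

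**Working it through.** **Inputs from section 1.6.** Control proportion 27%, UF proportion 16.88%, two-sided alpha 0.05, power 0.90, 432 patients per arm, 10% loss to follow-up, 13% crossover.

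**The plan's own figure.** The unpooled Z formula gives n per arm = (1.960 + 1.282)² × [0.27 × 0.73 + 0.1688 × 0.8312] / (0.27 − 0.1688)² = 346.2. This rounds up to 347 per arm, or 694 in total. Then 694 × 1.10 = 763.4, so 764, and 764 × 1.13 = 863.3, so 864. All three stated totals reproduce. The loss allowance is 0.10 × 432 = 43.2, about 43 per arm.

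**Test used.** Section 1.1 specifies a Wald test from logistic regression. Without the stratification covariates this is z = log OR / SE. Here log OR = ln(UF events / UF non-events) − ln(control events / control non-events), and SE = √(sum of the reciprocals of the four cells).

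**A borderline result (assumed counts).** Control 117/432 (27.1%, the planned rate), UF 96/432 (22.2%).

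- All randomised: log OR = ln(96/336) − ln(117/315) = −0.262, SE = 0.158, z = −1.66, p = 0.098.
- 16 event-free controls left out (117/416 = 28.1%): log OR = ln(96/336) − ln(117/299) = −0.314, SE = 0.159, z = −1.98, p = 0.048.

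Event-free patients are the right ones to vary, because a patient with a recorded event already has a determined binary outcome.

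| Event-free patients left out | p |
|---|---|
| none | 0.098 |
| 15 controls | 0.0503 |
| 16 controls | 0.048 |
| 20 controls | 0.039 |
| 5 UF | 0.119 |
| 20 UF | 0.206 |
| 43 in each arm | 0.092 |

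The size and direction of the shift depend on how the exclusions differ between arms. Balanced exclusion of the full loss allowance hardly moves p.

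**Away from the boundary.** At the planned effect (117 v 73 events of 432), p = 0.0003. Removing 26 control patients with an event gives p = 0.045 and removing 27 gives p = 0.053, so 27 are needed to lose significance. With equal arms (117 v 117), 33 UF patients with an event must go before p falls below 0.05.

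**The case against.** The strongest case on the other side is that the plan already limits discretion. The safety set is all randomised patients. Section 1.1 fixes the denominator as those randomised. Lost patients have a stated rule and an imputation analysis. The per-protocol analysis is supportive only. Sections 1.2 and 1.4 defer further detail to a statistical analysis plan, so rules for the meeting may be given there. These points stand, and they narrow the problem to the completeness condition and the sentence on the meeting. They do not remove it, because the rules that protect the denominator contradict the definition of the set on which the primary test is run.

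Three stronger readings are tempting, and the documents do not support them.

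- A reader might infer that the meeting sees arm and outcome together. The text does not say so and does not use the word unmasked. It is silent on timing and masking; visibility of the arm is a fair inference from the treatments, no more.
- A reader might infer that crossovers can also be dropped from the primary analysis. Section 1.5 rules this out: "treatment crossovers will be analyzed according to the intention to treat principle and thus will be included in the arm to which they were randomized". They are exposed only in the per-protocol set.
- A reader might infer that removing very few UF patients with events could decide the trial. Near the boundary the arithmetic allows it, but the completeness condition gives little ground for excluding a patient whose event is recorded. Removing event-free UF patients moves p away from significance.

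**Conclusion.** The point holds for the primary set. Its definition conflicts with section 1.1 and with the sentence that follows it, and it opens the primary analysis to exclusions based on post-randomisation data, settled at a meeting with no stated safeguards. The consequence is confined to borderline results: in the worked case, an excess of about 16 event-free exclusions in the control arm crosses 0.05. The planned effect would survive. These figures rest on assumed event counts at the planned control rate, an unadjusted test, and exclusions concentrated in one arm. The lack of masking and of a definition of major deviations affects the per-protocol set, where it is mainly missing detail. The change should be made.

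**What to change.** 1. In section 1.5, end the definition of the ITT set after the word randomized, deleting the completeness condition. State that patients are analysed in their assigned arm, and drop the word modified.
2. State that the ITT and safety sets involve no assignment at the data review meeting.
3. Handle missing primary outcomes by the stated rules: status at withdrawal for the main analysis and multiple imputation as sensitivity analysis. Make the missing-data paragraph in section 1.4 agree with this. No patient is excluded for missing data.
4. For the per-protocol set only, list the major deviations in advance. Make any remaining judgement on listings that hide arm and primary outcome, signed off before these are merged in.

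The cost is wording and a set of masked listings, with no extra patients and no change to clinical procedures. One small downside is that deviations which reveal the arm must be graded by rule and not by discussion. If a masked review is already intended, the plan need only say so.

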### **1.6.** SAMPLE SIZE JUSTIFICATION

Previously published results from clinical trials comparing intravenous loop diuretics to mechanical fluid removal by isolated veno-venous ultrafiltration have yielded conflicting results regarding heart failure-related rehospitalization. The present PURE-HF study is similar to the AVOID-HF (Costanzo et al., 2015) in terms of study design and targets. The primary objective of the AVOID-HF study was to determine whether UF prolonged the time to first HF event within 90 days of hospital discharge. Regarding sample size considerations, the AVOID-HF trial refers to different publications in order to provide an estimate of the combined HF event rate for the control group and the assumed reduction of the HF event rate in the UF group (Felker et al., 2011, O'Connor et al., 2011, Costanzo et al., 2007, Konstam et al., 2007, Hernandez et al., 2010, Ross et al., 2010).

Taking into account the assumptions and observations actually made in the prematurely terminated AVOID-HF study published by Costanzo et al. (Costanzo et al., 2016) we estimated that 864 patients (432 in each arm) should be sufficient to test whether there is a difference between the event proportions of the test and the control treatment. The proposed sample size calculations based on the two-sided Z test with unpooled variance and include the following assumptions: 1)  $\alpha$  of 0.05 ( $\alpha$ /2=0.025); 2) power (1- $\beta$ ) of 0.90; 3) an HF event rate for the loop diuretics group of 25% plus 2% cardiovascular death and 4) a reduction of the event proportion for the UF group of 37,5 % (this leads to an event proportion for the UF group of 16,88%). The estimated total sample size is displayed with additional patients included to account for 10% of subjects lost to follow-up and 13% treatment failures due to crossover during the treatment period

Event proportion			Sample size N		
control group	UF group	Reduction	Crude	Incl. 10% loss to FU	Incl. 10% loss to FU and 13% treatment failure
27.00%	16.88%	37.50%	694	764	864

- 1) Test for two proportions,
- 2) two-sided a of 0.05,
- 3) power of 0.90,
- 4) HF event rate of control group of 25% + 2% in-hospital death
- 5) an event proportion for the loop diuretics group (control group) of 27%,
- 6) an event proportion for the UF group (treatment group) of 16.88% (37.50% reduction),
- 7) including 10% loss to follow up and 13% crossover (i.e. treatment failure),

The sample size calculation was carried out using PASS 14 [PASS 13. NCSS, LLC. Kaysville, Utah, USA. www.ncss.com.]

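### Section 1.6 adds the 10% loss allowance by multiplying instead of dividing: 764 should be 772, which carries to about 874 rather than 864, at a cost of less than one point of power

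*Combined protocol and SAP*

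**What the plan says.** Section 1.6 bases the calculation on a "two-sided Z test with unpooled variance", with "two-sided a of 0.05" and 90% power. The control proportion is 27%, built from "an HF event rate for the loop diuretics group of 25% plus 2% cardiovascular death". The effect is "a reduction of the event proportion for the UF group of 37,5" percent, and the list under the table repeats it as "an event proportion for the UF group (treatment group) of 16.88% (37.50% reduction").

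The table then gives three totals: 694 crude, 764 with 10% loss to follow-up, and 864 with 10% loss and 13% treatment failure. The text explains the second and third: "The estimated total sample size is displayed with additional patients included to account for 10% of subjects lost to follow-up", and then for crossover during treatment.

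The list under the table describes the control rate a second time: "HF event rate of control group of 25% + 2% in-hospital death". The text calls the same 2% cardiovascular death.

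**The concern.** An allowance for loss should leave the required number of patients once the loss has occurred. If a fraction d is lost, the number randomized must be n/(1 − d). Multiplying by (1 + d) always falls short, because the fraction is then lost from the larger number. The table's middle row appears to use the multiplying form, so it does not do what its label says, and the error passes into the 864 given in the synopsis and in section 1.6.

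At stake are the accuracy of the published target and the stated 90% power. A smaller matter is the label of the 2%. The primary endpoint counts cardiovascular death to 90 days after randomization but heart failure events only after discharge. Cardiovascular death to 90 days and death in hospital are different quantities, and a reader cannot tell which one was assumed.

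**Working it through.** **Inputs, all from section 1.6:** p1 = 0.27; p2 = 0.1688; two-sided α = 0.05 (z = 1.960); power 0.90 (z = 1.282); equal arms; 10% loss; 13% treatment failure.

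**1. Reproduce the crude figure.** With unpooled variance,

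n per arm = [p1(1 − p1) + p2(1 − p2)] × (1.960 + 1.282)² / (p1 − p2)²

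= (0.1971 + 0.1403) × 10.51 / 0.1012² = 346.2, rounded up to 347.

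The total is 694, as stated. The method and rates are therefore the plan's own, and what follows does not come from a different formula.

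**2. Reproduce the enlarged figures.**

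- 694 × 1.10 = 763.4, rounded up to 764 (as stated).
- 764 × 1.13 = 863.3, rounded up to 864 (as stated).

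Both steps multiply.

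**3. Test the loss row against its purpose.**

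- 764 × 0.90 = 687.6, so about 687 remain, against 694 required.
- 694/0.90 = 771.1, rounded up to 772.
- Check: 772 × 0.90 = 694.8, which meets the requirement.

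The row is 8 patients short (772 − 764).

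**4. Carry it through.** Keeping the plan's second step, 772 × 1.13 = 872.4, rounded up to 873, or 874 for two equal arms of 437. The final total is 10 short with equal arms (874 − 864), about 1%.

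**5. Power on the stated rates.** Power = Φ{ (p1 − p2) / √([p1(1 − p1) + p2(1 − p2)]/n) − 1.960 }, with n per arm.

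| Basis | n per arm | Power, 27% v 16.88% |
|---|---|---|
| Crude requirement, 694 | 347 | 90.1% |
| 764 less 10%, about 687 | 343 | 89.7% |
| 864 less 10% and less 13%, about 677 (864 × 0.90 × 0.87 = 676.5) | 338 | 89.3% |
| 864 less 10% only, about 778 (864 × 0.90 = 777.6) | 389 | 93.0% |

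The third row takes both allowances as patients lost to the analysis, which is how the table handles them. The fourth assumes that crossover has no effect at all.

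**6. Optional sensitivity figure (not a stated input).** Suppose the 37.5% reduction applied to heart failure events only and the 2% deaths were unchanged. The ultrafiltration proportion would be 0.25 × 0.625 + 0.02 = 17.63%. Power would then be 84.7% with 694 analysed (347 per arm), and 88.5% with 864 less 10% loss and no crossover effect (389 per arm).

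**The case against.** **The loss error is immaterial.** It amounts to 8 patients in its own row and 10 in the final total, and under one point of power. This stands as to size. It does not make the row correct: the table still shows a number that falls short of its own requirement.

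**Lost patients are not simply removed.** Section 1.5 says that subjects lost to follow-up are analysed on their status at withdrawal, with multiple imputation as a sensitivity analysis. If all of them enter the analysis, the number analysed does not fall by 10%. This stands in part only. The same paragraph restricts the population to subjects with complete efficacy data, and section 1.6 itself adds patients because some will be lost.

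**A stronger reading: the 90% power fails because the reduction is also applied to deaths.** A reader might infer this because section 1.6 mentions "the assumed reduction of the HF event rate in the UF group". That phrase describes what the earlier trial's sample-size reasoning drew on. For this trial, the fourth assumption, the list and the table all apply 37.5% to the 27% composite event proportion, and 694 follows exactly. The 84.7% and 88.5% in step 6 test a different assumption and do not show an error on the plan's own inputs.

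**Crossover matters more.** Section 1.5 keeps crossovers in the arm to which they were randomized, so they would dilute the effect rather than reduce the number analysed. That is a separate question about the 13% step. It neither causes nor cures the error in the 10% step.

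**Conclusion.** The 10% loss row is wrong: 764 should be 772, and 864 becomes about 874 if the × 1.13 step is kept. The size is small. On the plan's rates, power is 89.7% at 343 per arm, and about 89.3% when both allowances are taken as attrition from 864, against the stated 90%. These figures rest on the plan's 27% and 16.88%, its unpooled Z test, and lost patients not contributing to the analysis.

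This does not show a trial that is materially underpowered on its stated inputs. Nor should a power of about 84% be quoted as that of the planned 864 before crossover: the 84.7% belongs to 694 analysed patients under an assumption the plan does not make.

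The two labels for the 2% are a real inconsistency and should be reconciled. The documents do not show which one was meant.

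**What to change.** Either of two changes to section 1.6 settles the arithmetic:

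- Correct the loss row to 694/0.90 = 772 and carry it through to about 874 (437 per arm), with the matching change in the synopsis. This raises the target by 10 patients.
- Keep 864 and restate the power as about 89%, saying that both allowances are treated as attrition. This needs no extra patients.

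Give the 2% one label in the text and in the list. If the sponsor wishes, add the calculation with deaths unchanged as a sensitivity figure, stating the number analysed beside each power (84.7% with 694; 88.5% with 864 less 10% loss, before any crossover effect). With the second option the cost is wording and figures in one section; conduct and the analysis do not change.
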